# Study Protocol

Name of the project:	International name: PIMPmyHospital (local name: PIMPmyHUG)
Name of the institution:	Geneva Children's Hospital, Geneva University Hospitals
Name of the PI:	[name]
Affiliation	Children's Hospital, Geneva University Hospitals, [name], contact: [contact]
National Clinical Trial Identifier Number	NCT05203146
Registered on	Jan 21, 2022
Funding	None
Sponsor	None
Version number	v.1.0, Jul 15, 2021
Objective(s)/Aim:	To assess the impact of a newly developed mobile application (PIMPmyHospital) on pediatric emergency physicians and nurses to improve remote collaborative and synchronous communication in a pediatric emergency department (via a chat messaging system) and to reduce the time spent walking/traveling in between destinations (emergency rooms, etc.) when caring for patients, when compared to current methods not using the mobile app. This app aims to provide relevant information in real-time about the patients they care for, as well as a secure chat and messaging platform to virtually connect physicians and nurses caring for the same patients.
Outcome/Endpoints	
Primary outcome  The time taken (in minutes, within a upper time limit set at 120 minutes) for each allocation group to consider new laboratory results, whether accessed through the mobile app or the institutional Electronic Health Record (EHR) patient data system, from the point of availability to participant review on the designated medium (mobile app or EHR).
 
Secondary outcomes  The time elapsed (in minutes, within a upper time limit set at 120 minutes) from the notification received by the participant through the mobile app or a statement from a study investigator (conventional method), indicating that a nurse needed assistance for a technical procedure, up to the moment when the participant reached the designated nurse.

Project design and procedures	
This will be a single-center, non-blind, two-arm, randomized, controlled pilot trial. This study aims to assess two methods for processing laboratory results (specifically, the post-analytical phase) and facilitating collaborative actions in standardized, semi-simulated scenarios mimicking everyday situations within a Pediatric Emergency Department (PED). Participants will be randomly allocated to perform these actions either utilizing the dedicated mobile app PIMPmyHospital (intervention group) or employing conventional methods (i.e., the EHR, control group). The primary hypotheses posited that the use of the mobile app would result in a reduction in both the time taken to access laboratory results and the time required for remote communication with colleagues.
 
The trial will take place in a real-world environment at the Pediatric Emergency Department (PED) of the Geneva Children's Hospital, Switzerland, during caregivers' shifts, but no patients will be enrolled, nor

[figure not shown]
	
their medical data collected. The recordings will not be used for any purpose other than this project.
 
The trial will be registered on Clinicaltrials.gov.

Project population, inclusion and exclusion criteria	
A convenience sample of 10 caregivers. Eligible participants will be postgraduate residents pursuing a <6-year residency in pediatrics and registered nurses from the PED of the Geneva Children's Hospital (aged > 18 years). They must have previously completed a standardized 5-minute introductory course on app usage provided by the study investigators on the day of participation. Exclusion criteria encompass participants who have not completed the introductory course. Recruitment of participants adheres to Cohen's calculation, with an anticipated effect size of 2.0, a type I error of 0.05, and a power of 80%.

Recruitment, screening and informed consent procedure	
Participants will be recruited from the PED of the Geneva Children's Hospital. On the day of participation, in the presence of the study investigators, participants will provide informed consent, provided they had ample time for consideration and opportunity to ask questions. No financial compensation will be offered to participants.

Involvement of samples or health related data	
No patients will be enrolled in this trial. Hence, no patient's samples or data will be collected.

Randomization and Blinding	
Participants will be randomized using a single, constant 1:1 allocation ratio determined through web-based software www.sealedenvelope.com. Allocation concealment will be maintained with the use of the allocation software, and it will not be released until participants initiate the scenario. To minimize preparation bias, participants will be kept unaware of the scenario during recruitment. Following randomization at the scenario's commencement, they will be unblinded to their assigned study arm. The study investigators involved in the scenario, assuming the role of a fellow nurse to be located by participants, will be revealed to participants before the scenario begins. All investigators will remain uninformed about the outcomes until all data are unsealed for analysis at the conclusion of the trial.

Intervention	
Following randomized allocation, participants will complete a brief demographic survey on the day of participation. Subsequently, they will undergo a standardized 5-minute training session on mobile app usage, designed solely to explain its functionality for the upcoming intervention. To maintain study integrity, the PED signage and layout will remain unaltered, taking into account participants' presumed familiarity with their daily working environment after a minimum of 3 months of common PED assignment.
 
Participants will then encounter a semi-simulated scenario involving a fictitious patient combined with real clinical activities. Retrieving simulated patient laboratory results from the EHR, participants will have the option to use the app or the institutional computerized system without app support. After obtaining results, participants will be tasked with locating a nurse, played by a study investigator, either prompted by an app message or an oral request from a second investigator. Assessing the app's impact on remote communication, this task will address communication challenges in a PED. No nurse location information will be given; participants will have to physically find the nurse, prohibiting virtual contact. Procedures will be standardized to ensure consistent exposure to the same case, minimizing preparation bias. The app will be interfaced on an Apple iPhone X, with identical functionality on Android OS. Data access will be restricted to study investigators.
 
The functionalities of the mobile app have been previously published (PMID: 34734879)

Confidentiality	Information about study subjects will be kept confidential. All data will be entered into a Microsoft Excel spreadsheet where all data on study subjects are assigned an individual identifying code that does not contain identifying information.
Are the samples/data irreversibly anonymized?	
YES. Data will be saved in duplicate on secured hard disk drives in a locked cabinet at the Geneva Children's Hospital.
 
All electronic patient data exchanged between the institutional computerized patient record (i.e., the Geneva University Hospital servers) and the app is secured. No patient data will be used as an outcome or for analysis. Only the time taken by participants to access the data will be recorded and analyzed.

Withdrawal and discontinuation	Withdrawal and discontinuation will be limited since this study offers the advantage of taking place in a single center and during a single, short intervention period during a regular working day within the emergency department. In case of withdrawal after informed consent, individual's collected data so far and related to the intervention will be destroyed/deleted. Any withdrawal and/or discontinuation will be justified and reported in final publications in coded form.
Statistics	The Statistical Analysis Plan (SAP) is attached to the study protocol submitted on clinicaltrials.gov
Regulatory aspects and safety	
 
Local regulations / Declaration of Helsinki The research project will be conducted in accordance with the protocol, the Declaration of Helsinki [PMID: 24141714], the principles of Good Clinical Practice [PMID: 10532877].
 
Notification of safety and protective measure The study investigators anticipate no circumstances that could compromise patient safety, given the project's design, which does not involve patient enrollment and does not expose participants to risks beyond those of their daily practice throughout the course of this study.
 
Serious events No serious events are anticipated. Study investigators do not foresee the need to implement any specific security measures
 
Risk-Benefit assessment Risks to project participants are minimized as the intervention is integrated into their routine clinical practice. The only real difference, devoid of any risk, will be the procedure using a mobile app rather than conventional methods to retrieve lab results and communicate with colleagues. Risk of unauthorized data access and/or unwanted identification of project participants will be guaranteed by using Microsoft Excel software secured by protected access passwords and hosted by the Geneva University Hospitals on secured servers. No direct benefits are anticipated for study participants.
 

Overall ethical considerations	According to the International Committee of Medical Journal Editors and SwissEthics (i.e., the National Ethic board in Switzerland), the trial protocol received a declaration of no objection by SwissEthics and the Geneva institutional ethics committee (Switzerland) since the purpose of the study will be to assess the effect of the intervention on healthcare providers and not on patients.

Will this project generate generalizable knowledge?	YES. The goal of this study is to generate evidence-based data in order to be able to deploy this mobile app in the near future within the University Hospitals of Geneva, and beyond to other hospitals.  To date and to the best of our knowledge, no study has measured such data and for the same purpose as this trial.
Is it solely a quality control for institution-internal purposes	This is a pilot randomized controlled trial to assess the impact of a newly developed mobile app on caregivers' work efficiency, and aimed to improve patient-centered care.
Prior submission to an Ethics Committee?	The preliminary evaluation study of the app PimpMyHospital via semi-structured interviews was accepted by SwissEthics on July 2nd 2021 (Req-2021-00740).

Date and signature:

14 July 2021

 A handwritten signature in black ink, appearing to be a stylized 'P' or a similar character, is written over the date '14 July 2021'.

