# Statistical Analysis Plan

Name of the project:	International name: PIMPmyHospital (local name: PIMPmyHUG)
Name of the institution:	Geneva Children's Hospital, Geneva University Hospitals
Name of the PI:	[name]
Affiliation	Children's Hospital, Geneva University Hospitals, [name], contact: [contact]
National Clinical Trial Identifier Number	NCT05203146
Registered on	Jan 21, 2022
Funding	None
Sponsor	None
Version number	v.1.0, Jul 15, 2021
Statistical analyses	
For the primary outcome, we will assess the time taken in minutes for each allocation group to consider new laboratory results, whether accessed through the mobile app or the institutional Electronic Health Record (EHR). Normality analysis of continuous variables will be performed using the Shapiro–Wilks test. Given the anticipated non-normal distribution of data, the Mann–Whitney test will be employed for comparing independent groups. No paired data will be compared. Kaplan–Meier curves will be estimated, and bivariate survival analysis will use the log-rank (Mantel–Cox) test.
 
For the secondary outcome, we will assess the time taken in minutes from the participant's notification, either through the mobile app (intervention) or a statement from a study investigator (conventional method), indicating the need for assistance with a technical procedure, to the participant reaching the designated nurse. Similar analyses will be conducted for the secondary outcome.
 
All statistical tests will be two-tailed with a significance level of 5%. Data analysis will be carried out using Prism latest software version (GraphPad software, LLC., San Diego, CA, USA) for MacOS.

Interim analysis	We will not perform interim analyses as our trial has a short duration and no potential serious outcomes.
Handling of missing data	In the case of missing data, a complete case analysis will be conducted. No multiple imputations are planned.
Statistical tests	All statistical tests will be two-sided with a type I error risk of 5%. Data analysis will be carried out using GraphPad Prism latest software version for MacOS (GraphPad software, San Diego, CA, USA) for graph figures, descriptive statistics, and statistical tests.

Date and signature:

14 July 2021

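### The stated 80% power fits a t-test on normal data; the planned Mann-Whitney test, done exactly at 5 v 5, has about 68% for the same effect

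*Protocol*

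**What the plan says.** **Sample size.** The protocol (Project population, inclusion and exclusion criteria) plans "A convenience sample of 10 caregivers" and attributes the number to Cohen's calculation, with "an anticipated effect size of 2.0, a type I error of 0.05, and a power of 80"%. It gives no test, mean difference or SD.

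**Allocation.** Under Randomization and Blinding: "Participants will be randomized using a single, constant 1:1 allocation ratio". With 10 people this is read as 5 v 5.

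**Analysis.** The SAP (Statistical analyses) says: "Given the anticipated non-normal distribution of data, the Mann–Whitney test will be employed for comparing independent groups". For the same outcome it adds Kaplan-Meier curves and says "bivariate survival analysis will use the log-rank (Mantel–Cox) test". The secondary outcome is to be analysed in the same way. Under Statistical tests: "All statistical tests will be two-sided with a type I error risk of 5"%. The SAP does not say whether the Mann-Whitney p-value is exact or approximate.

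Neither document gives a power for the Mann-Whitney or the log-rank test.

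**The concern.** A power statement belongs to a particular test under a particular distribution. Cohen's effect size is a mean difference in SD units, and the usual calculation built on it is a t-test on normal data. The SAP sets that model aside and uses a rank test.

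In large samples the switch would cost little. With five per arm a rank test has few attainable p-values, and its true level can fall well below 5%. The quoted 80% may therefore not apply to the analysis that will be run. If so, a non-significant result would be read against a power worked out for a different test, in a trial whose protocol says its purpose is evidence for deploying the app in Geneva and elsewhere.

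**Working it through.** **Inputs.** N = 10, d = 2.0, alpha 0.05 and stated power 80% come from the protocol's population section; the 1:1 ratio from Randomization and Blinding; two-sided testing, Mann-Whitney and log-rank from the SAP. Assumptions added here: 5 v 5, no ties, and no observation cut at the 120-minute limit.

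**Step 1: reproduce the 80%.** For a two-sided t-test the noncentrality is d × √(n/2) = 2.0 × √2.5 = 3.16 on 2 × 5 − 2 = 8 degrees of freedom. The noncentral t distribution gives power 0.7905, and solving for exactly 80% gives n = 5.09 per arm. Other readings do not fit five per arm: the normal approximation gives 88.5% and a one-sided t-test 89.2%. That the stated figure is a two-sided t-test is an inference from this arithmetic.

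**Step 2: rejection region of the exact Mann-Whitney test.** There are C(10,5) = 252 equally likely orderings under the null. Let U be the smaller of the two Mann-Whitney counts. In one tail, U = 0, 1, 2, 3 arises in 1, 1, 2 and 3 orderings.

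- U ≤ 2: 2 × (1 + 1 + 2) = 8, and 8/252 = 3.17%.
- U ≤ 3: 2 × (1 + 1 + 2 + 3) = 14, and 14/252 = 5.56%, above 5%.

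The exact test at 5% therefore rejects only for U ≤ 2.

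**Step 3: power under the model behind Cohen's d.** One arm is N(0,1) and the other N(2,1). Mann-Whitney and best-rank-test rows use 3,000,000 simulated trials; log-rank rows use 400,000.

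| Test at 5 v 5 | True level | Power |
|---|---|---|
| t-test (step 1) | 5.0% | 79.1% |
| Exact Mann-Whitney (U ≤ 2) | 3.2% | 67.6% |
| Uncorrected normal-approximation Mann-Whitney (U ≤ 3) | 5.6% | 78.1% |
| Log-rank, chi-square p-value | 18/252 = 7.1% | 78.5% |
| Log-rank, permutation p-value | 12/252 = 4.8% | 73.0% or 74.6%, by choice of statistic |
| Best symmetric two-sided rank test within 5% | 12/252 = 4.8% | 74.8% |

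The miss probability for the exact Mann-Whitney test is 100 − 67.6 = 32.4%. It reaches 80% at d of about 2.31 (simulated 79.9%). Using ranks costs about one point (79.1 to 78.1); the coarse null distribution costs the other 10.5 (78.1 to 67.6).

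**Step 4: the p-value method matters.** The null SD of U is √(25 × 11/12) = 4.79 around a mean of 12.5. At U = 3 the uncorrected z is (3 − 12.5)/4.79 = −1.98, p = 0.047. With continuity correction it is (3.5 − 12.5)/4.79 = −1.88, p = 0.060. The exact p is 0.056. Only the uncorrected version rejects; the corrected one has the same rejection region as the exact test.

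**Step 5: other distributions (exact Mann-Whitney).** These shapes are assumptions, since the documents name none.

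| Alternative | Power |
|---|---|
| 2 SD shift, uniform | 64% |
| 2 SD shift, logistic | 69% |
| 2 SD shift, exponential | 70% |
| 2 SD shift, lognormal, log-SD 0.2 to 1.0 | 69% to 79% |
| Lognormal ratio, raw-scale d = 2, log-SD 0.2, 0.3, 0.4, 0.5 | 72%, 77%, 85%, 95% |

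In the last row the two arms have unequal SDs, and d uses the root mean square of the two.

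**The case against.** **The 68% rests on conditions the SAP does not set.** It needs normal data, which the SAP expects not to have, and an exact p-value, which the SAP does not specify. This stands as a limit: 68% is a benchmark, not a prediction. It does not rescue the 80%, which rests on the same normal model. The exact test stayed below 80% for every 2 SD shift tried. Some lognormal ratio effects do exceed 80%, but that depends on how d is defined: with the faster arm's SD the same four cases give 53%, 48%, 44% and 41%.

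**The planned log-rank test is the ordinary chi-square version, with 78.5% power.** At 5 v 5 without ties, every ordering that the exact Mann-Whitney test rejects is also rejected by the chi-square log-rank test, so the chance that at least one rejects is 78.5%. That is correct, but its true level is 7.1%, above the SAP's own 5%. The miss probability of 32% applies when the exact Mann-Whitney test decides.

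**The t-test basis and the 5 v 5 split are inferred.** True. No other reading tried gives 80% at five per arm, and 5 v 5 is the plain result of 10 people at 1:1.

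**This is a small pilot, and an assumed effect of 2.0 has no stated source.** This lowers the weight of the point and argues against demanding more participants. The protocol nevertheless makes a formal power claim and the SAP plans formal 5% tests, so the claim should match the test.

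**Conclusion.** The concern holds. The stated 80% fits a two-sided t-test on normal data (79.1% at 5 v 5). Under the same normal shift of 2.0 SD, the exact two-sided Mann-Whitney test has 67.6% power at a true level of 3.2%, about 12 points below the stated figure. No symmetric two-sided rank test that respects a true 5% level exceeds about 75% there, so the log-rank test does not close the gap.

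The size rests on 5 v 5, an exact p-value, a normal shift, no ties and no cut at 120 minutes. Under other distributions power may be lower or higher. This should be fixed, but it does not undermine the design.

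**What to change.** In the protocol, replace the power statement with wording such as:

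> With 5 participants per arm, the exact two-sided Mann-Whitney test (attained level 3.2%) has about 68% power for a standardised difference of 2.0 under a normal shift, and 80% power for about 2.3; power differs for other distributions.

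In the SAP, state that the exact Mann-Whitney p-value will be used, and that the power statement refers to this test and not to the log-rank test. Fixing the p-value method in advance also removes a choice that would decide significance at U = 3.

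The cost is one sentence in each document and a less favourable stated power. The correction needs no extra participants. If the investigators prefer to keep the 80% target, 6 v 6 (12 caregivers) gives 82.8% with the exact test under the same normal shift.

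### Does it matter that the protocol places randomisation both before the app training and at the start of the scenario?

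*Protocol*

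**What the plan says.** Three parts of the protocol bear on the order of events.

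- **Intervention.** The section begins "Following randomized allocation, participants will complete a brief demographic survey on the day of participation. Subsequently, they will undergo a standardized 5-minute training session" and then moves to the scenario. Allocation comes first, followed by survey, training and scenario.
- **Randomization and Blinding.** The sentence on unblinding opens "Following randomization at the scenario" and goes on to name the scenario's start as the moment. The same section says of the allocation that "it will not be released until participants initiate the scenario".
- **Project population, inclusion and exclusion criteria.** On eligibility: "They must have previously completed a standardized 5-minute introductory course on app usage provided by the study investigators on the day of participation". The one stated exclusion is the converse: "Exclusion criteria encompass participants who have not completed the introductory course". The planned size is "A convenience sample of 10 caregivers".

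Consent is taken the same day: "On the day of participation, in the presence of the study investigators, participants will provide informed consent". The SAP, under Handling of missing data, provides for a complete-case analysis and names no analysis set for someone randomised and later found ineligible.

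**The concern.** A randomised trial should have one identifiable point of randomisation, and this protocol gives two. The Intervention section puts it before training. The Randomization and Blinding section puts it after.

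The eligibility rule makes this look more serious. The course required for entry and the training in the Intervention section share their length, their topic, their day and the label of being standardised. If they are one session, the Intervention order leaves the only stated exclusion unresolved when the participant is randomised. Exclusion after randomisation can undo the balance that randomisation provides, particularly if those who know the assigned arm can influence who is dropped. In a trial of 10 people there is little room for that. The SAP would handle such a person only through its complete-case rule, and the protocol's Withdrawal and discontinuation section does not say whether an exclusion for ineligibility counts among the events to be reported.

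**Working it through.** The plan attaches no figure to this point, so there is nothing to reproduce. The check is to set the passages side by side and ask what could go wrong under each reading.

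**Step 1: is the conflict real?** The Intervention section places the scenario after training. Randomisation at scenario start is therefore after training, and allocation ahead of the survey is before it. An allocation drawn early and held back would satisfy the Intervention section and the release rule, but not the phrase dating randomisation itself to the scenario's start. The conflict stands, though it rests on that phrase.

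**Step 2: where could exclusion follow randomisation?**

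| Order followed | Course and training are one session | Two separate sessions |
|---|---|---|
| Randomization and Blinding | No: training is finished first | No |
| Intervention | Yes, possible | No, if the course was completed before allocation, as the eligibility wording suggests |

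One cell of four is affected.

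**Step 3: in that cell, could exclusion depend on the arm?** Two provisions bear on this.

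- The allocation is held in the web-based software and is not released until the scenario begins. At training, the arm is not known.
- The training and the eligibility rule are written for all participants, so both arms go through the same step.

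Completion of the training is therefore independent of allocation. Among completers, the assigned arm is still determined by chance alone.

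**Step 4: could it affect the outcome data?** Both outcomes are timed during the scenario. A non-completer never reaches it and so has no time to discard. The complete-case rule would compare the remaining participants as randomised, without bias from this source.

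**Step 5: how large is what remains?** One exclusion would be 1/10 = 10% of the planned sample. The documents give no non-completion rate and no replacement rule, so neither a probability of exclusion nor a loss of power can be derived from them. The session lasts 5 minutes, is run by the investigators and falls on the day of consent, so non-completion should be rare.

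**The case for a change.** The strongest case for acting is that the correction is nearly free. Removing the opening words of the Intervention section and saying whether the course and the training are the same would leave one sequence, and every step already falls on the same day. With 10 participants, each one matters, and the SAP gives no explicit rule for a person randomised and then found ineligible.

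Part of this stands. The wording conflict is real. It could be removed by reading the Randomization and Blinding sentence as placing only the unblinding, and not the randomisation, at scenario start, but that strains the text. The course and the training are very probably one session.

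The step from there to a consequence does not stand. The eligibility wording requires the course to have been completed previously. Read as an entry condition, it agrees with the Randomization and Blinding section and leaves the opening words of the Intervention section as the outlier. A team following the protocol has a workable sequence: train, confirm eligibility, then randomise and release. If the team instead drew the allocation early, the release rule would still protect the comparison. Any difference in the count would be visible from reporting how many were randomised and how many analysed, and the protocol already promises to justify and report withdrawals and discontinuations.

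**Conclusion.** No change to the plan is needed. The two sections disagree on when randomisation happens, but this is a clerical inconsistency, and following either one leaves the comparison sound. At worst, the number randomised exceeds the number analysed, by 10% of the planned sample for each person affected, without favouring either arm.

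This rests on two assumptions: that the release rule is kept for the investigators running the training as well as for participants, and that non-completion of a 5-minute session is rare. The first is what the protocol's concealment statement provides. The second is a judgement, since the documents give no rate. That the course and the training are one session is likely but unstated. If they are separate, the exclusion route closes and only the difference in wording remains.

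### Does the word 'option' in the Intervention section leave open which medium each arm uses and which review stops the primary clock?

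*Protocol*

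**What the plan says.** The Protocol, under Project design and procedures, assigns one medium to each arm. Participants are randomised to act "either utilizing the dedicated mobile app PIMPmyHospital (intervention group) or employing conventional methods (i.e., the EHR, control group". Under Randomization and Blinding, once the scenario starts "they will be unblinded to their assigned study arm". The Risk-Benefit assessment describes the only difference from routine work as "the procedure using a mobile app rather than conventional methods to retrieve lab results".

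The Intervention section is less careful. For retrieving the simulated results it says "participants will have the option to use the app or the institutional computerized system without app support", and it names no arm.

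The primary outcome in the Protocol runs "from the point of availability to participant review on the designated medium (mobile app or EHR", with an upper limit of 120 minutes. The SAP, under Statistical analyses, describes the time "for each allocation group to consider new laboratory results, whether accessed through the mobile app or the institutional Electronic Health Record (EHR". It does not repeat the start point, the stop point or the term *designated medium*. Neither document says what happens if a participant first sees the result on the medium of the other arm.

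**The concern.** An option is not an allocation. If app-arm participants could freely choose the EHR, the comparison would no longer be app against EHR, and the endpoint would be ambiguous in a way that matters. One reading stops the clock at the first review on either medium. The other waits for review on the allocated medium, even if the result has already been read elsewhere, and could run to 120 minutes.

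The scenario takes place during real shifts, and no sentence bars the app arm from the EHR. The sample is 10 caregivers, so about five per arm, and the handling of one person could decide the primary test. A rule that can decide the result should not be chosen after the data are seen.

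**Working it through.** **Reading the text.** Four places bear on which medium each arm uses.

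1. Project design and procedures: app for intervention, EHR for control. This is explicit.
2. Randomization and Blinding: participants learn an assigned arm. A free choice of medium would leave that assignment without content.
3. Risk-Benefit assessment: app in place of conventional methods. This is the same contrast.
4. Intervention: the sentence with *option*. The next task in the same paragraph is described in the same either/or form, the prompt being an app message or an oral request. The secondary outcome ties that prompt to the arm (app, or the conventional method). The paragraph names no arms at all; it lists both conditions together. *Without app support* describes the control condition.

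Three places fix the medium by arm, and the fourth fits them once it is read as covering both arms. *Designated medium* is then the allocated one: its gloss lists the same two media that the design section assigns.

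Access on the assigned medium also matches the stated aim. The design section's hypothesis concerns the time to access results, and the anonymisation row of the Protocol says that access time is what is recorded and analysed.

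**What one off-arm read could do.** The inputs from the documents are 10 participants, 1:1 allocation, effect size d = 2.0, two-sided 5% and 80% power (Protocol), and the Mann-Whitney and log-rank tests (SAP).

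The plan's own figure comes first. By the normal approximation, n per arm = 2(1.96 + 0.84)²/2² = 3.92, rounded up to 4. By the noncentral t with 5 per arm, df = 8 and noncentrality 2 × √(5/2) = 3.16, power is 79.1%. The stated 10 therefore reproduces to within a point of 80%.

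For the exact Mann-Whitney test at 5 v 5 there are C(10,5) = 252 arrangements. U ≤ 2 covers 4 of them, so p = 2 × 4/252 = 0.032. U ≤ 3 covers 7, so p = 2 × 7/252 = 0.056. The test therefore rejects at U ≤ 2.

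The following are assumptions, not taken from the documents: normal times with SD 1, app mean 0, control mean 2, and exactly one of five app-arm participants reading on the EHR, with a time drawn from the control distribution. The app-control mean difference then falls from 2.0 to 2.0 × 4/5 = 1.6. Simulated power at d = 2:

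| Handling of that one participant | Exact Mann-Whitney | Log-rank |
|---|---|---|
| No such participant | 68% | 78% |
| Timed at the EHR read | 32% | 40% |
| Dropped (5 v 4) | 60% | 78% |
| Set to 120 min, no control at the limit | 0% | 0% |

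The zero for the Mann-Whitney test follows by counting. With four app times below all controls and one above them all, U = 5. U ≤ 5 covers 19 arrangements, so the smallest p is 2 × 19/252 = 0.151. This case needs the participant never to open the app within 120 minutes and no control to reach the limit. If all five controls also reached it, the smallest p would be 0.048.

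For d = 1.5, 2.5 and 3.0, exact Mann-Whitney power is 43%, 86% and 95% with no case, 22%, 39% and 45% at the EHR time, and 37%, 79% and 91% if dropped.

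The log-rank column uses asymptotic p-values, which reject too often at this size (about 6.8% under the null at 5 v 5 and 7.9% at 5 v 4). The two 78% entries therefore do not show that dropping a participant costs nothing.

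**The case for a change.** The strongest case for a change accepts that the medium is allocated and rests on the missing rule alone. Reading *designated* as *allocated* does not remove the difficulty: an app-arm participant who has already read the result on the EHR would keep accruing time. The Intervention section bars virtual contact in the nurse task but states no matching restriction for the laboratory task. The table shows that handling one person can decide the test, and a sentence of text is cheap.

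Part of this stands. The *option* sentence is loosely worded, the link between *designated* and the arm is left to inference, and no rule covers an off-arm read.

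The rest is weaker. Analysis by allocation is already indicated, since the SAP says "we will assess the time taken in minutes for each allocation group to consider new laboratory results" and the Protocol's outcome uses the same unit. Neither document proposes dropping anyone, so the *dropped* row tests a rule that nobody has suggested. The main substantive remedy, first review on either medium, is a choice between endpoints. It measures when the information was first seen by any route, and at d = 2 it gives 32% power instead of 68% in the very case it is meant to handle. Timing access on the assigned medium is equally defensible for a pilot about accessing results through an app.

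**Conclusion.** The concern does not call for a change. The allocation of the medium is fixed in the design section and supported in two other places; the *option* sentence is a slip of wording. What remains is missing detail on an event that may never occur: an app-arm participant reading the result first on the EHR. An analyst would fill it sensibly from the text, by keeping everyone in the allocated group, timing review on the allocated medium and reporting any departure.

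The size is conditional. If one of five app-arm participants did this, exact Mann-Whitney power at d = 2 would lie anywhere between 0% and 60% depending on handling, against 68% otherwise. These figures rest on an assumed single case, normal times and, where the participant is timed at the EHR read, a time drawn from the control distribution. The documents give no frequency for the event. The figures show how fragile a comparison of five against five is; they do not show an error in the plan. Run on the allocation as written, the primary comparison is sound.
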